5.1.1.2 Management for Treatment-Related Toxicity of ramucirumab

Adverse events of concern which may be related with ramucirumab include are infusion-related reactions, hypertension, arterial or venous thromboembolic events, bleeding (hemorrhagic) events, proteinuria, cardiac events, gastrointestinal perforation, anemia, surgery and wound healing liver injury/liver failure, and reversible posterior leukoencephalopathy syndrome (RPLS). Listed below are guidelines on how to manage these toxicities. Dose reductions of ramucirumab will be allowed only for proteinuria with 6 mg/kg for first episode of proteinuria (2-3 g/24 hours) and with 5 mg/kg for second episode of proteinuria (2-3 g/24 hours) (details on table 2 and **5.1.1.2.4**). Only dose delay will be allowed for the other AEs related to ramucirumab.

5.1.1.2.1 Infusion related reactions

For the treatment of infusion related reaction, institutional protocol can be used. If there is no institutional protocol, the following can be used for treatment of ramucirumab infusion-related reactions.

Grade	Management
Grade 1	
 • Slow the infusion rate by 50% • Monitor the patient for worsening of condition • For subsequent infusions, premedicate with diphenhydramine hydrochloride 50 mg I.V.; additional premedication may be administered at the investigator's discretion
Grade 2	
 • Stop the infusion • Administer diphenhydramine hydrochloride 50 mg I.V., acetaminophen 650 mg orally for fever and oxygen • Resume the infusion at 50% of the prior rate once the infusion-related reaction has resolved or decreased to Grade 1; the infusion duration should not exceed 2 hours • Monitor the patient for worsening of condition • For subsequent infusions, premedicate with diphenhydramine hydrochloride 50 mg I.V.; additional premedication may be administered at the investigator's discretion

Grade 3	
 Stop the infusion and disconnect the infusion tubing from the patient Administer diphenhydramine hydrochloride 50 mg I.V., dexamethasone 8-10 mg I.V. (or equivalent), bronchodilators for bronchospasm, and other medications/treatment as medically indicated Patients who have a Grade 3 infusion-related reaction will be discontinued from study
Grade 4	
 Stop the infusion and disconnect the infusion tubing from the patient Administer diphenhydramine hydrochloride 50 mg I.V., dexamethasone 8-10 mg I.V. (or equivalent), and other medications/treatment as medically indicated. Give epinephrine or bronchodilators as indicated Hospital admission for observation may be indicated Patients who have a Grade 4 infusion-related reaction will be discontinued from study

For a second Grade 1 or 2 infusion-related reaction, administer dexamethasone 8-10 mg I.V.; then, for subsequent infusions, premedicate with diphenhydramine hydrochloride 50 mg I.V., acetaminophen 650 mg orally, and dexamethasone 8-10 mg I.V. (or equivalent)

5.1.1.2.2 Hypertension

- If patients develop hypertension during the study, they should be treated with antihypertensive medications according to standard medical practice.
- The following are treatment guidelines for ramucirumab related hypertension

Grade	Management
Grade 1 or 2	
 If the hypertension is not associated with symptoms, continue ramucirumab and initiate antihypertensive therapy If the hypertension is associated with symptoms, hold ramucirumab until symptoms resolve and initiate antihypertensive therapy
Grade 3	
 For Grade 3 hypertension not associated with symptoms, continue ramucirumab with more intensive antihypertensive therapy. If systolic BP remains ≥ 160 mm Hg or diastolic BP ≥ 100 mm Hg > 2 weeks after initiation of additional antihypertensive therapy, hold ramucirumab while continuing appropriate antihypertensive therapy If the hypertension is associated with symptoms, hold ramucirumab until symptoms resolve and initiate

	antihypertensive therapy
Grade 4	
 ○ Patients with Grade 4 hypertension (life-threatening consequences, eg, malignant hypertension, transient or permanent neurologic deficit, hypertensive crisis; or urgent intervention indicated) or patients whose hypertension is poorly controlled (> 160 mm Hg systolic or > 100 mm Hg diastolic for > 4 weeks) despite (> 2 oral agents at MTD) will be discontinued from study therapy.

5.1.1.2.3 Thromboembolic events

- Investigators should perform all testing required to fully characterize arterial or venous thrombotic/vascular events.
- Ramucirumab should be discontinued in the event of any Grade 3-4 arterial thromboembolic event or any Grade 3-4 venous thromboembolic event that is considered by the investigator to be life-threatening, or symptomatic and not adequately treated by anticoagulation therapy.
- At the investigator's discretion, ramucirumab may be continued in this setting of an incidentally diagnosed asymptomatic deep vein thrombosis or pulmonary embolism, or following a symptomatic deep vein thrombosis or pulmonary embolism when symptoms have resolved with the institution of anticoagulation therapy.
- In the event that a patient experiences a Grade 4 pulmonary embolism or a Grade 3-4 venous thromboembolic event that is considered by the investigator to be life-threatening, or symptomatic and not adequately treated by anticoagulation therapy, the patient will not receive further ramucirumab and be discontinued from study therapy.
- Ramucirumab should also be discontinued, and a patient will be discontinued from study therapy in the setting of a deep vein thrombosis or pulmonary embolism that occurs or intensifies while the patient is receiving therapeutic anticoagulation therapy.

5.1.1.2.4 Proteinuria

If, while on ramucirumab, a patient has proteinuria $\geq 2+$ per a dipstick or routine urinalysis test, ramucirumab will continue as scheduled, and a 24-hour urine collection will be conducted prior to the subsequent scheduled treatment in 2 weeks.

- The following are treatment guidelines for ramucirumab related proteinuria

Proteinuria	Management
< 2g/24hours urine	
 Continue on ramucirumab at the same dose without interruption
2-3g/24hours urine (first episode)	
 Hold ramucirumab for 2 weeks Repeat a 24-hour urine collection prior to next infusion. Resume ramucirumab at a reduced dose level (6 mg/kg every 2 weeks) once the protein level returns to < 2 g/24 hours.
2-3g/24hours urine (second episode)	
 Hold ramucirumab for 2 weeks Repeat a 24-hour urine collection prior to next infusion. Resume ramucirumab at a reduced dose level (5 mg/kg every 2 weeks) once the protein level returns to < 2 g/24 hours.
2-3g/24hours urine (third episode) or >3g/24hours urine	
 Discontinue ramucirumab

5.1.1.2.5 Hemorrhagic events

Serious hemorrhagic adverse events have been reported from clinical studies investigating ramucirumab.

- The following are treatment guidelines for ramucirumab related hemorrhage

Grade	Management
Grade 1 or 2	
 Continue ramucirumab
Grade 3 or 4	
 Discontinue ramucirumab

5.1.1.2.6 Gastrointestinal perforation events

An infrequent incidence of gastrointestinal perforations has been associated with some antiangiogenic therapeutic agents. These events may be associated with extensive abdominal/peritoneal disease burden. Gastrointestinal perforation has been reported from clinical studies investigating ramucirumab. Ramucirumab should be discontinued in the setting of any gastrointestinal perforation.

5.1.1.2.7 Reversible posterior leukoencephalopathy syndrome (RPLS)

- Reversible posterior leukoencephalopathy syndrome (RPLS) is a clinical and radiologic syndrome typically consisting of reversible cortical neurological dysfunction and brain-imaging findings of subcortical edema involving the posterior circulation, particularly the occipital lobes. The symptoms of RPLS most often include generalized seizures, headache, delirium, and cortical blindness, although these may vary significantly and occasionally include focal neurological deficits. Magnetic resonance imaging (MRI) represents the most reliable method for the diagnosis. Clinical symptoms and MRI abnormalities usually recover within days to weeks with proper management, although permanent neurologic dysfunction has been reported.
- Because hypertension is an identified risk for ramucirumab, investigators should control BP. In addition, investigators should consider a diagnosis of RPLS in the setting of seizures, headache, nausea, delirium, visual changes, and/or other unexplained neurological symptoms, especially in combination with hypertension and MRI findings of hyperintensity on T2-weighted and fluid-attenuated inversion recovery images
- If the diagnosis of RPLS is confirmed, ramucirumab DP should be permanently discontinued.

5.1.1.2.8 Cardiac events

- Patients with symptomatic CHF, unstable angina pectoris, or symptomatic or poorly controlled cardiac arrhythmia should not be enrolled in this study.
- Ramucirumab should be discontinued in the event of any Grade 3-4 events consistent with CHF.

5.1.1.2.9 Surgery and impaired wound healing

- Surgery and impaired wound healing have been observed with some antiangiogenic agents.
- Ramucirumab will not be administered to patients who have undergone major surgery within 28 days or have undergone central venous access device placement within 7 days prior to ramucirumab administration.
- Patients with postoperative and other nonhealing wound complications are excluded, as are patients for whom major surgical procedures are planned.

5.1.1.2.10 Liver injury/liver failure

- Patients with Child-Pugh B cirrhosis (or worse), any degree cirrhosis, a history of hepatic encephalopathy, clinically meaningful ascites from cirrhosis, new occurrence of hepatic encephalopathy and/or hepatorenal syndrome from liver cirrhosis. Ramucirumab should be discontinued following a new occurrence of hepatic encephalopathy and/or hepatorenal syndrome resulting from liver cirrhosis.

5.2 Concomitant therapy

- All patients should be maintained on the same medications throughout the study period, as medically feasible;
- The investigator should instruct the patient to notify the study staff about any new medications he/she takes after the start of the study drug. All medications (other than study drug) and significant non-drug therapies (including physical therapy and blood transfusions) administered after the patient starts treatment with study drug must be recorded;
- Administration of pegfilgrastim or filgrastim following initiation of protocol therapy is at investigator's discretion for all patients;
- Administration of erythropoietin or darbopoietin is allowed;
- Administration of bisphosphonates is permitted at the investigator's discretion
- Transfusions of red blood cells, platelets, or other blood products are permitted at the investigator's discretion
- Patients must be instructed not to take any additional medications (including herbal supplements and over-the-counter products) during the trial without prior consultation with the investigator. All medications taken within 30 days of screening should be recorded. If concomitant therapy must be added or changed, the reason and name of the drug/therapy should be recorded;
- In general, the use of any concomitant medication/therapies deemed necessary for the care of the patient are allowed, including drugs given prophylactically (e.g. antiemetics or steroids).
- Premedication is recommended before ramucirumab administration (including first dose). Recommended premedication agents include histamine H1 antagonists such as diphenhydramine hydrochloride 50 mg I.V. (or equivalent). Additional premedication may be provided at the investigator's discretion.

5.2.1 Prohibited Concomitant Medications

Subjects are prohibited from receiving the following therapies during the Screening and Treatment Phase of this trial:

- Antineoplastic systemic chemotherapy, immunotherapy or biological therapy not specified in this protocol
- Investigational agents other than TAS 102 or ramucirumab
- Radiation therapy

Subjects who, in the assessment by the investigator, require the use of any of the aforementioned treatments for clinical management should be removed from the trial. Subjects may receive other medications that the investigator deems to be medically necessary.

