4.3 Withdrawal of Subjects from Study

Subjects **must be withdrawn from the trial** (treatment and procedures) for the following reasons:

- Subject withdraws consent from study treatment and study procedures. A subject must be removed from the trial at his/her own request or at the request of his/her legally acceptable representative. At any time during the trial and without giving reasons, a subject may decline to participate further. The subject will not suffer any disadvantage as a result.
- Pregnancy. Pregnancies will be reported to Taiho within 24 hours of having knowledge of the event. Pregnancy will not be reported as an SAE but the subject must be withdrawn from the trial immediately. (Note: subjects who have been withdrawn from treatment with study drug because of pregnancy should not undergo CT scans [with contrast]/MRI or bone scans while pregnant.)
- If, in the investigator's opinion, continuation of the trial would be harmful to the subject's well-being.
- Subject is lost to follow-up.
- Death.

All subjects who discontinue should comply with protocol specified follow-up and survival procedures. The ONLY exception to this requirement is when a subject withdraws consent for all

study procedures or loses the ability to consent freely (i.e., is imprisoned or involuntarily incarcerated for the treatment of either a psychiatric or physical illness). If a subject was withdrawn before completing the study, the reason for withdrawal must be entered on the appropriate case report form page.

Subjects **may be** withdrawn from study treatment for the following reasons:

- The subject is non-compliant with TAS 102 administration, ramucirumab administration, or trial procedures; including the use of anti-cancer therapy not prescribed by the study protocol.
- Severe allergic reaction to TAS 102 or ramucirumab.
- The development of a second cancer.
- Development of an illness or situation which would, in the judgment of the investigator, significantly affect assessments of clinical status and trial endpoints.
- Deterioration of ECOG performance status to 3 or 4.
- Use of illicit drugs or other substances that may, in the opinion of the investigator, have a reasonable chance of contributing to toxicity or otherwise skewing trial result.

Any subject removed from the trial will remain under medical supervision until discharge or transfer is medically acceptable.

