4.3.1 Screen Failures/Dropouts/Replacements

A subject who discontinues study participation prematurely for any reasons except death, disease progression and severe toxicity is defined as a dropout.

A subject who, for any reason (e.g., failure to satisfy the selection criteria), terminates the study before the time point used for the definition of "dropout" (see above) is regarded a "screening failure".

Subjects who withdraw from treatment (for any reason) may be replaced.

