4.3.2 Patient Replacement

Dropout (see 4.3.1 for definition of "dropout") patients will need to be replaced.

Patients will be replaced if they come off treatment without any response evaluation for reasons other than drug related AE or disease progression.

5. Treatment Plan

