9.2 Determination of sample size

The primary objective of this study is overall survival at 6 months. Overall survival (OS) will be defined as the time from starting on trial to date of death due to any cause. Dropouts/screen failures defined in section 4.3.1. Patients will be considered inevaluable for the primary endpoint of 6 months of overall survival if they are not able to complete first cycle or if they are lost follow-up prior to 6 months from starting on trial except death. Inevaluable patients will be replaced. The study will test the null hypothesis of $\leq 45\%$ of OS at 6 month against the alternative of $\geq 70\%$ of OS at 6 month. The sample size was determined based on the Simon's two-stage minimax design. With one-sided 10% of type I error rate and 90% power, a sample of evaluable 25 patients will be evaluated; 15 in first stage and additional 10 patients in second stage. If 7 or more out of 15 survive 6 months or more, the study goes on the second stage. The experimental treatment will be deemed to have good activity if ≥ 15 out of 25 patients survive 6 months or more. We will continue to recruit patients during interim analysis

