9.3 Statistical analysis

Overall survival (OS) is defined as the time from starting on trial to date of death due to any cause and progression-free survival (PFS) is defined as the duration of time from start of treatment to time of progression or death, whichever comes first. The final analysis will be conducted after the follow-time of the last patient exceeds 6 months. The primary endpoint of the study is OS at 6 month. The experimental treatment will be deemed to have good activity if ≥ 15 out of 25 evaluable patients survive 6 months or more. OS will be estimated using the Kaplan-Meier method and the two-sided 95% confidence interval (CI) for median OS will be computed using log-log transformation.

The secondary endpoints in this study include toxicity, PFS and the objective response rate (ORR) defined as (complete response (CR) + partial response (PR)) using RECIST 1.1 criteria (Appendix A). ORR will be reported with 95% CI computed by the Clopper-Pearson method. The frequency and severity of adverse events and tolerability of the regimen will be summarized using descriptive statistics. PFS with 95% CI will be estimated. As exploratory objective, the association between biomarkers and clinical outcomes (ORR, OS and PFS) will be examined using multiple logistic regression and the multivariable Cox regression model. A p-value of <0.05 will be considered statistically significant. Frequency and severity of adverse events will be summarized using descriptive statistics.

10. Data Recording

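### Sections 9.2 and 4.3.2 replace treated patients whose 6-month survival can still be known, such as one removed under 5.2.1 for radiotherapy, and after cycle 1 no text says which section decides who is in the 25

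*Combined protocol and SAP*

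**What the plan says.** Section 5.2.1 prohibits radiotherapy, with no restriction by site, during screening and treatment. Patients who in the investigator's assessment "require the use of any of the aforementioned treatments for clinical management should be removed from the trial".

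Four other sections determine what follows.

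- **4.3.1:** "A subject who discontinues study participation prematurely for any reasons except death, disease progression and severe toxicity is defined as a dropout". It adds an optional rule that anyone who withdraws from treatment may be replaced.
- **4.3.2:** dropout "patients will need to be replaced", with no time limit and no reference to known survival status. A second sentence reads "Patients will be replaced if they come off treatment without any response evaluation for reasons other than drug related AE or disease progression".
- **9.2:** the first ground for exclusion reads "Patients will be considered inevaluable for the primary endpoint of 6 months of overall survival if they are not able to complete first cycle". The second is loss to follow-up before month 6, with an exception for death. Patients excluded on either ground are to be replaced. The section mentions the dropouts of 4.3.1 only in a fragment that states no consequence.
- **9.3:** the treatment is judged active if at least 15 "out of 25 evaluable patients survive 6 months or more".

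On follow-up, 4.3 states: "All subjects who discontinue should comply with protocol specified follow-up and survival procedures". The only exceptions are withdrawal of consent for all procedures and loss of the ability to consent freely. Section 6.7 opens the survival phase at confirmed progression or at the start of new anti-cancer therapy. It names no other reason for stopping treatment and does not say whether radiotherapy counts as such therapy.

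**The concern.** The primary endpoint is death from any cause by 6 months, counted from starting on trial. Stopping study treatment does not make that outcome unknowable, and the plan itself asks for survival follow-up to continue. Replacing a treated patient whose vital status can be obtained therefore discards an outcome for a reason that arose after treatment began. In an open-label single-arm trial, the investigator's judgement triggers the removal and no control arm offsets the selection.

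The decision turns on whether 15 of 25 patients survive, so the membership of the 25 should be settled before any outcome is known. If patients who leave survive less well than the rest, replacing them favours a positive result. If they survive better, it works against one.

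**Working it through.** **Who leaves the count.** Take a treated patient removed for radiotherapy, without progression or severe toxicity, whose vital status is followed.

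| Time of removal | 4.3.2 | 9.2 and 9.3 |
|---|---|---|
| Before cycle 1 is completed | Replaced | Inevaluable and replaced: explicitly out of the 25 |
| After cycle 1 | Dropout, replaced | Neither ground for inevaluability applies: still evaluable |

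The sections agree in the first row and diverge in the second, and no text ranks them. The same holds for any removal that is not due to death, progression or severe toxicity. The death exception in 9.2 follows the loss-to-follow-up clause. This point does not depend on whether it also covers death in cycle 1.

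**The plan's own figures.** The inputs from 9.2 are 15 patients then 10 more, continuation with at least 7 of 15, success with at least 15 of 25, a null of 0.45 and an alternative of 0.70. The chance of success at true rate p is

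P(p) = sum over x = 7 to 15 of Bin(x; 15, p) × Pr[Bin(10, p) ≥ 15 − x].

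This gives P(0.45) = 0.0951 and P(0.70) = 0.9004, which agree with the stated 10% and 90%. The sample size is not in question.

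**Effect of replacement.** Let q be the fraction of enrolled patients who leave the count and s their 6-month survival. The documents give neither, so both are assumptions. With overall survival held at the null, the rate among counted patients is

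p = (0.45 − q·s) / (1 − q).

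Two examples:

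- q = 0.05, s = 0.20: (0.45 − 0.01)/0.95 = 0.4632, and P = 0.1197.
- q = 0.05, s = 0.60: (0.45 − 0.03)/0.95 = 0.4421, and P = 0.0822.

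False-positive chance (%):

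| q | s = 0.20 | 0.30 | 0.40 | 0.50 | 0.60 |
|---|---|---|---|---|---|
| 1% | 9.95 | 9.77 | 9.59 | 9.42 | 9.25 |
| 2% | 10.41 | 10.04 | 9.68 | 9.33 | 8.99 |
| 5% | 11.97 | 10.94 | 9.97 | 9.06 | 8.22 |

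At s = 0.45 the figure stays at 9.51 for every q.

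**Where 10% is crossed.** P reaches 0.10 at p = 0.4528. Solving for q gives q = (0.4528 − 0.45)/(0.4528 − s):

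- s = 0.20: 1.1%, or 0.28 of 25 patients
- s = 0.30: 1.8%, or 0.46 of 25
- s = 0.40: 5.3%, or 1.33 of 25

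At s of 0.45 or above it is not crossed through this route.

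**Cycle 1 only.** Suppose 2-5% are removed but only the cycle 1 share leaves the count, taken as one-third (an assumption). Then q is 0.67-1.67%, and the chance is 9.6-10.3% for s of 0.20 to 0.40.

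**The case against.** The strongest reply is that 5.2.1 is an ordinary prohibited-therapy rule and that 9.2 already settles the matter. Section 9.2 alone defines evaluability for the primary endpoint, and 9.3 counts evaluable patients. A followed patient who completed cycle 1 therefore stays in, whatever 4.3.2 says about enrolment. That is the natural reading, and most of this objection stands: the defect lies in 9.2 and 4.3.2, and 5.2.1 is one trigger. What survives is that cycle 1 exclusion is explicit, and that 4.3.2 is mandatory and unranked.

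Section 4.3 also lists use of non-protocol anti-cancer therapy only as a reason why a patient may be withdrawn from treatment. On that text the patient might still be participating and so not be a dropout. Section 5.2.1 points the other way by removing the patient from the trial, so the documents are ambiguous.

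The affected group is small. Many patients who need radiotherapy will have progressed and are not dropouts, and exclusion criterion 20 already bars those who need radiotherapy to target lesions.

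Three stronger readings are tempting, and the documents support none of them.

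- *The false-positive chance exceeds 10%.* This needs survival among those who leave to be below the 45% average. They are patients without progression or severe toxicity, and nothing says that they do worse.
- *Patients removed after cycle 1 fall out of the 25.* No text says so; 9.2 and 9.3 suggest the opposite.
- *A replaced patient and the replacement both count.* With 26 patients and the cut-off still at 15, the chance would be 13.2%, but 9.3 fixes the denominator at 25.

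**Conclusion.** The point holds as a minor one. Followed as written, the plan excludes a treated patient who does not complete cycle 1 even when 6-month vital status is known. After cycle 1 it orders a replacement without saying whether the replaced patient still counts.

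The size and the sign of any bias are unknown. Against a design value of 9.5%, 2-5% leaving gives 9.7-12.0% if their survival is 20-40%, and 8.2-9.3% if it is 50-60%. At 1% leaving, the chance stays within 10% across that whole survival range. The figures assume overall 6-month survival of exactly 45% and that every patient in q is dropped and replaced. The effect is probably small. The case for a change is that one patient can decide between 14 and 15 survivors, and the rule for counting that patient should be fixed beforehand.

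**What to change.** Five wording changes:

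1. **5.2.1:** replace removal from the trial with discontinuing study treatment and remaining in survival follow-up.
2. **9.2:** state that a treated patient removed under 5.2.1 whose 6-month vital status is known counts in the 15 and the 25, including when cycle 1 is not completed, and is not replaced for the primary endpoint.
3. **4.3.2:** state that 9.2 decides who counts for the primary endpoint.
4. **6.7:** extend the survival follow-up trigger with *or discontinues study treatment for any reason*.
5. **Sections 3 and 5.1:** state that if one of the first 6 patients leaves before day 28 without a dose-limiting toxicity, the next enrolled patient supplies that observation.

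A change to 5.2.1 alone would leave 9.2 and 4.3.2 contradicting it. The sample size, the cut-offs, the radiotherapy prohibition and exclusion criterion 20 stay as they are. The cost is a few extra telephone contacts and possibly a slightly lower observed 6-month survival rate. No extra patients are needed, because the substitute toxicity observation comes from the planned 25.
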